# Emergency Medicine Prospective Protocol

against regression to the mean in RCT studies, which will be our approach when analyzing only a single follow-up (e.g. 12 months). However, when analyzing multiple follow-ups within the same model, using this baseline adjustment across the board (i.e. at every time point) can result in overestimation of the treatment effect; baseline adjustment for only the first follow-up corrects this overestimation while also guarding against regression to the mean, which will be our approach. We will also conduct exploratory tests of the interaction between time and treatment group, to see whether there is strong evidence that the treatment effect diminishes over time, which will inform future studies.

**SubAim:** We will determine moderators (caregiver sex, race, child age) of the intervention effects and mediators (Self-Determination Theory constructs of autonomy, relatedness, competence; emotional state at ED recruitment). We hypothesize that disparities in CRS use can be reduced through a tailored intervention that increases autonomous motivation, competence, and relatedness for correct CRS use. **Statistical Analysis:** **Moderation:** Within the GLM(M) modeling framework described above, we will evaluate moderation by including interactions between treatment group and sex-, race-, and age-based groupings. We will test whether sex as a biologic variable modifies the intervention effect, but will be underpowered to detect differences because children are infrequently with a male caregiver when seeking emergency care (10-15% in our pilot data). **Mediation:** We will use Imai's counterfactual mediation method, a very general framework that takes models for the outcome and mediator as inputs, to estimate mediation effects. Traditional mediation analysis can be susceptible to bias due to model misspecification and design limitations and limitations in the classes of statistical models, that can be accommodated (typically linear regressions for both the mediator and outcome) but the Imai framework can accommodate a wide variety of distributions for both the mediator and the outcome; our initial specification will be a logistic model for the binary variables and a linear (Gaussian) model for the numeric variables. We will use a quasi-Bayesian approach to draw from conditional distribution of the mediator given the "treatment" and other covariates, and that of the outcome given the exposure, mediator, and other covariates, to construct hypothesis tests for the proportion mediated; this approach is robustly implemented in the R package mediation.

**Aim 2:** To use latent growth curve models to identify characteristic trajectories for the CPaSS observed in digital photographs over the 12 study months and assess for correlates of the trajectory types. We hypothesize that caregivers will have different CPaSS trajectories in response to the basic intervention, the enhanced intervention, and the control condition. We expect to identify at least four patterns of response. **Statistical Analysis:** We will determine 12-month CPaSS trajectory types using adaptations of finite mixture models for the case where the units are trajectories. We will define trajectory shapes through methods combining semiparametric regression modeling (e.g., generalized additive models), with latent class regression, using the R package flexmix. Following convention, we will use the Bayesian Information Criteria (BIC) to determine the appropriate number of latent classes, while also making practical considerations to avoid overfitting, such as not allowing overly small groups to be created, as in previous applied work. Using the posterior probability of class membership, we place individuals into trajectory groups and treat that grouping as the outcome in a subsequent multinomial regression model to determine correlates of class membership, including treatment group, caregiver race/ethnicity, and child age group. If substantial uncertainty in class membership is found, outcomes in the multinomial model will be weighted accordingly.

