## **2.2 Secondary Objectives**

Additionally, we will determine moderators (caregiver sex, race, child age) and mediators (Self-Determination Theory constructs of autonomy, relatedness, competence; emotional state at ED recruitment) of the intervention effects at 12-month follow-up.

Finally, we plan a cost analysis of the intervention to inform wider dissemination and implementation in settings outside of the ED. We will measure the total costs of the intervention from participant and health system perspectives by gathering estimates of intervention resource requirements, including personnel costs, implementation time, participant time, and material costs. We will calculate costs of the intervention per child. Net costs (savings) will be calculated by subtracting mean costs per participant in the control condition from mean costs per participant who receive the basic TCBD and the enhanced TCBD interventions. We will also estimate cost-effectiveness as measured by dollars per caregiver using a size-appropriate CRS and using the CRS correctly

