# Emergency Medicine Prospective Protocol

- If the family did not visit the LCH ED, then the RC will not use EPIC to record any information. The parent enrolled will provide the study with the necessary information in the screening survey.
- Screening survey: If a child's parent/legal guardian chooses to be screened for eligibility in the full study, they will complete a short survey (~10 min.) on a study iPad or remotely on their own personal device. The survey will ask about their safety behaviors for kids in and around cars. It will ask about how their child usually rides in cars too. They should answer all questions for the child that is getting care at Lurie Children's. All answers are private, meaning they will not be shared with anyone outside of the study team.
- Baseline survey: If the child's parent/legal guardian screens eligible for the full study and consents to participate, they will complete a (baseline) survey on an iPad or remotely on their own device. This will take about 15-20 minutes. The survey will have questions about their use of car seats, and thoughts on child safety in and around vehicles. If they cannot finish the survey in person, they will have 5 business days to do this survey over the phone with a staff member or on their own device.
- After they get done with the survey, they will be randomly assigned (like flipping a coin) to one of two groups. They cannot pick the group that they will be in. The groups are:
  - Group 1 (Control --Usual Care): A study team member will give them an informational handout --see section 9 of IRB app "supporting document" for the PDF called, "Study Handout"

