## ***3.2 Allocation to Interventional Group***

After completing the baseline survey, all caregivers will be randomized into one of two groups: 1) TCBD intervention group, or 2) control group. Computerized, block randomization (block sizes from four to eight) will be applied to assign eligible caregivers to the TCBD intervention or control group in a 3:1 ratio. Blocks will be stratified by age groups related to child passenger safety recommendations (<2 years – rear-facing CRS, 2-4 years – forward-facing CRS, 5-10 years – booster seat) and the child passenger safety behavior that led to eligibility for study (not using the recommended restraint currently or planning a premature transition in the coming 6 months).

After the 6-month follow-up assessment, caregivers in the intervention group only who continue suboptimal CRS use will be re-randomized by computer in a 1:1 ratio to receive either the basic or enhanced intervention. The enhanced TCBD will include one additional motivational interviewing (MI) session by phone in Month 7/8 and one to two additional tailored text messages in Months 7-12 (total of 7 tailored tips during these months compared to 4 tailored tips for those in the basic TCBD). The extra text messages will be sent to those in the enhanced TCBD group until size-appropriate restraint use is observed. Caregivers receiving enhanced TCBD will be encouraged to obtain a free seat check with a certified child passenger safety technician (CPST) in the community. The primary outcomes (size-appropriate CRS use and CPaSS) will be assessed in-person at Months 6 and 12. The secondary outcome, the CPaSS trajectory, is a measure of correct and consistent restraint use in response to the intervention and will be assessed by scoring photographs submitted by caregivers (Months 1-5; 7-11).

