## **3.3 Study Measures**

Over the course of this study, participants will complete the following surveys: screen, baseline, 6- and 12-month survey. At the 6-month follow-up, the participants will also complete a brief health literacy assessment called the Newest Vital Sign.

The selected measures for the surveys are reliable, valid, and have been pilot tested in the study population. Measures will be assessed at screening, baseline and re-assessed at the 6- and 12-month follow-up visits. Assessments will be self-administered or RC facilitated on a study iPad in the ED and at in-person follow-up assessments (Months 6 and 12). Skip patterns will reduce administration time. Our team has found baseline assessment lasting 20 minutes to be feasible and acceptable to caregivers in the ED setting during pilot testing.

Table 1 illustrates survey measures for this study along with the frequency/timing of assessments.

Table 1: Measures	Assessment Month(s)
OUTCOMES	
Primary Outcome	
Size Appropriate Restraint Use (dichotomous)	6 and 12
Child Passenger Safety Score direct observation	6 and 12
Secondary Outcome	
Child Passenger Safety Score remote observation	ED/Baseline through 12
Exploratory Cost Measures	
Intervention Time (ED, Phone MI) for RA/Counselor	ED/Baseline and 2
Intervention Time (ED, Phone MI, texts, web app) for caregiver	ED/Baseline through 12
Material Costs - iPads, computers, maintenance	ED/Baseline through 12
Intervention Costs - Photograph review, texts, web app	ED/Baseline through 12
MODERATORS/MEDIATORS	
Caregiver Demographic Characteristics, reason for ED visit	ED/Baseline
Child Size	

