# Emergency Medicine Prospective Protocol

Measured weight and length/height	ED, 6, and 12
Self-Determination Theory Constructs	
Treatment Self-Regulation Questionnaire 	ED/Baseline, 6, and 12
Confident rulers and Perceived Competence Scale 	ED/Baseline, 6, and 12
Health Care Climate Questionnaire 	12 months
Health Literacy and Numeracy	
The Newest Vital Sign 	6 months
Caregiver Emotional State, Stress, Coping	
State-Trait Anxiety Inventory 	ED/Baseline
Risk Behavior Diagnosis Scale 	ED/Baseline
Parenting stress index	ED/Baseline
Marlowe-Crowne Social Desirability Scale 	6 months
Child Passenger Safety Hassles Scale 	ED/Baseline, 6, and 12

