## 6 Statistical Plan

### 6.1 Sample Size and Power Determination

Briefly, our calculations are based on two-sample comparisons between groups (e.g., control and TCBD) using results from our pilot study that assessed percent size-appropriate child passenger safety behaviors at 6-month follow-up (referred to as the “response rate” below). For analyses involving multiple time points, these calculations represent a conservative lower bound on the power that would only be achieved if the effective sample equals 1 observation per person (i.e. perfect within-individual correlation). For the calculations below we assume: a) 17% response rate among controls; b) 25% response rate among TCBD caregivers at 6 Month (with 75% of TCBD caregivers re-randomized); and c) only 80% of the target sample (n=204 controls and n=516 TCBD in the initial dichotomy) will be available for analysis at follow-up. Components (a) and (b) are based on pilot data where the control group received generic educational materials and outcomes were assessed at 6-months. Component (c) is a conservative correction for attrition. For Aim 2, we estimated power while accounting for uncertainty in the group sizes by simulating response and re-randomization patterns according to the above probabilities and testing for significant between-group differences; this process was repeated 10,000 times and the power was estimated as the percent of replications in which a between-group difference was identified. Binary Outcome: For the binary response case, if the observed response rate is at least 29.4% among those receiving enhanced TCBD, it can be reliably (>80% power) distinguished from a control response rate of 17%. Analogously, a response rate of at least 27.6% among basic intervention would be reliably (>80% power) distinguished from control. Converted to Cohen's  $h$ , both differences reflect small-to-medium effect sizes ( $h = 0.30$  and  $h = 0.26$ , respectively). Numeric Outcome (CPaSS): If the standardized mean difference (i.e. Cohen's  $D$ ) is  $>0.25$  (a small-to-medium effect size), we can reliably distinguish between control and basic TCBD conditions. Similarly, if  $D \geq 0.28$ , a small-to-medium effect size, we will have sufficient power (80%) to distinguish the control and enhanced TCBD conditions. Aim 2: Monte Carlo studies of linear latent trajectory models indicate that a medium level of heterogeneity among the slopes and/or intercepts of the trajectories can be reliably recovered (power  $> 80\%$ ) with a total sample size of  $n=200$ , with power exceeding 95% when the level of heterogeneity is high; given that our sample size soundly exceeds 200, we expect sufficient ability to determine the underlying characteristic trajectory types. Nevertheless, we further justify our sample size with a brief simulation study. Assuming a final sample size of 720, conservatively assuming individuals are only measured at an average of 25% of the 12 monthly assessments, we simulate data from a population with four equally likely trajectory types: consistently low, consistently high, linearly decreasing, and starting high then dropping off. Because we have no basis for estimating variability in the score, we assumed mean/variance equivalence, consistent with the Poisson distribution. Due to the time required to fit such models, we only completed 200 simulation replications, where we were able to correctly conclude (based on BIC) that there were four

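### Emotional state at ED recruitment is measured before randomisation, so it cannot mediate the intervention effect and should come off the mediator lists in 2.2 and 6.2

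*Combined protocol and SAP*

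**What the plan says.** The SubAim in section 6.2 lists "mediators (Self-Determination Theory constructs of autonomy, relatedness, competence; emotional state at ED recruitment". Section 2.2 gives the same list and ties it to the final assessment: "emotional state at ED recruitment) of the intervention effects at 12-month follow-up". Both sections list the moderators separately, as caregiver sex, race and child age, and the moderation paragraph of 6.2 plans interactions for those three only.

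Table 1 in section 3.3 has a joint heading, "MODERATORS/MEDIATORS". Under it is a block titled "Caregiver Emotional State, Stress, Coping", which contains the "State-Trait Anxiety Inventory", the Risk Behavior Diagnosis Scale and the Parenting stress index, all scheduled at ED/Baseline only. Two other measures in the block have later time points: social desirability (6 months) and the Hassles Scale (baseline, 6 and 12 months).

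On timing, the baseline visit description in section 3 says "After they get done with the survey, they will be randomly assigned", and section 3.2 says "After completing the baseline survey, all caregivers will be randomized into one of two groups". The study-groups text after 3.2 gives the same order.

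For mediation, section 6.2 specifies a counterfactual method with quasi-Bayesian draws. It models the mediator given treatment and tests the proportion mediated.

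**The concern.** A mediator lies on the path from treatment to outcome, so treatment must be able to move it. A score fixed before allocation cannot be moved by allocation. One of the four named mediators therefore cannot give an informative answer, whatever the data show.

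The risk is misreading. The method will still return an estimate and an interval. A chance difference between arms in baseline anxiety, or a difference produced by who stays in follow-up, would appear in the report as a share of the effect explained by emotional state. Elsewhere in 6.2 the plan treats significant baseline differences as something to adjust for; here the same kind of difference would be presented as mechanism.

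**Working it through.** **Timing.** Sections 2.2 and 6.2 fix the variable at ED recruitment. Table 1 gives the three scales no later time point. Sections 3 and 3.2 place randomisation after the baseline survey, including surveys finished within the 5-business-day window. So measurement precedes assignment.

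**True value.** Let M(1) and M(0) be a caregiver's score under intervention and control. Measured before assignment, M(1) = M(0) for everyone. The indirect effect is E[Y(t, M(1)) - Y(t, M(0))] = 0 for t = 0 and 1, and so the proportion mediated is 0 whenever the total effect is not 0. No numerical assumption is needed.

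**What the estimate would do.** The plan states no mediation figure to reproduce, so the rest is simulation.

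Inputs from section 6.1: "only 80% of the target sample (n=204 controls and n=516 TCBD in the initial dichotomy) will be available for analysis at follow-up". Hence 204/0.8 = 255 and 516/0.8 = 645 randomised, total 900, which matches section 4.2.

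Assumptions: standardised score M independent of arm at randomisation; numeric outcome Y = 0.25T + bM + e with Var(Y|T) = 1; linear mediator and outcome models; 1000 quasi-Bayesian draws per trial; 4000 trials per cell in the main run. The 0.25 is the plan's detectable difference for basic TCBD versus control, applied here to the pooled 516. The documents give neither the slope b nor a dropout pattern. Mediation on the binary outcome was not simulated.

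*(A) 204 vs 516 analysed, dropout unrelated to arm and score:*

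| Slope b | Indirect effect significant | Proportion mediated significant | 95% range of estimated proportion |
|---|---|---|---|
| 0 | 0.1% | 0.1% | not tabulated |
| 0.1 | 4.0% | 2.9% | about -10% to +9% |
| 0.3 | 4.7% | 3.1% | about -33% to +20% |
| 0.5 | 5.1% | 3.4% | not tabulated |

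The spread comes from chance imbalance. The standard error of the baseline difference is sqrt(1/204 + 1/516) = 0.0827 SD, so differences up to 1.96 × 0.0827 = 0.162 SD are unremarkable.

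*(B) 255 vs 645 randomised, 20% lost per arm, dropout log-odds rising by g per SD of score in the intervention arm only.* Rejection of the indirect effect, with ranges across repeat runs of 2000 or more trials:

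| Slope b | g | Mediator model on completers | Mediator model on all 900 |
|---|---|---|---|
| 0.3 | 0.3 | 11% to 12% | 5.5% |
| 0.3 | 0.5 | 23% to 24% | 5.5% |
| 0.1 | 0.3 | 7% to 8.5% | 3.7% |
| 0.1 | 0.5 | 14% to 16% | 3.2% |

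Across runs, the all-900 column lies at about 3% to 6%. The plan tests the proportion mediated, and for completers in the main run that rejects less often: 5.9% and 12.3% at b = 0.3, and 5.3% and 10.8% at b = 0.1. The median estimated proportion at b = 0.3 is negative, -7% and -13%. A significant positive indirect effect occurs in at most 0.25% of trials.

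**Power if the score is used as a moderator instead** (two-sided 0.05, 80% power, score standardised with equal spread in both arms):

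- Numeric outcome, residual SD 1: (1.96 + 0.842) × 0.0827 = 0.23 outcome SD per SD of score.
- Binary outcome, 17% vs 27.6% (section 6.1, the second again being the basic TCBD value): SE of the log ratio of odds ratios = sqrt(1/(204 × 0.17 × 0.83) + 1/(516 × 0.276 × 0.724)) = 0.211, and exp(2.80 × 0.211) = 1.81. By simulation, 80% power is reached at about 1.87 to 1.92. Power is about 18% at a ratio of 1.25 and 44% to 47% at 1.5.

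**The case against.** The strongest reply is that the harm is small. When dropout is unrelated to arm and score, no test rejects more often than about 5%. The hypothesis attached to the SubAim concerns autonomous motivation, competence and relatedness, and none is stated for emotional state. That stands. It lowers the weight of the point but does not make the analysis answer a question.

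A reader might infer from the completer figures that the plan will inflate false mediation claims. The documents do not support that. The score is collected before randomisation, so later dropout leaves it observed. Section 6.2 commits to including everyone randomised, and 8.2 allows multiple imputation. The mediation paragraph does not say which set the mediator model uses, so the inflation depends on an unstated analysis set as well as an invented dropout pattern. Under the assumed signs it also yields a negative proportion, not a mechanism that appears to explain a benefit. Reversing the sign of the slope or of the dropout relation would reverse this, and the documents fix neither.

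A reader might also infer that the plan has no other use for the variable. That goes too far. Table 1's heading covers both roles, 6.2 allows adjustment for imbalanced covariates, and the Aim 2 list of correlates is open-ended. What can be said is that no moderation test of it is explicitly planned.

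Two defences of the text fail. Section 3.3 says in general terms that measures are repeated at 6 and 12 months, but Table 1 gives these scales no repeat, and 2.2 and 6.2 name the value at recruitment. The Hassles Scale is repeated, but its later values are not emotional state at recruitment.

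**Conclusion.** The point holds, and it is narrow. As written, the plan assigns a pre-randomisation variable to the mediator role, where its true indirect effect is 0 by design. That rests only on the order of measurement and randomisation, which the documents state consistently.

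The practical size depends on assumptions. With dropout unrelated to arm and score, the result is uninformative noise at no more than about the nominal error rate. Rejection of the indirect effect at about 7% to 24% needs both a completer-only mediator model and score-dependent dropout in one arm.

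The primary comparison, the planned sex, race and age moderation, and the autonomy and competence paths, whose scales are repeated after randomisation, are unaffected. The correction should be made before mediation results are produced.

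**What to change.** Delete the reference to emotional state at ED recruitment from the mediator lists in 2.2 and 6.2. That alone cures the error and costs two wording changes.

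Optionally, to use data already collected, state which Table 1 scale represents emotional state (three baseline-only scales sit under that heading) and add one arm-by-baseline interaction per primary outcome, with the score kept continuous and the tests labelled exploratory. This is a choice, not part of the cure. It adds two secondary tests, one for each primary outcome. On the binary outcome, 80% power is available only for a large interaction, a ratio of odds ratios of about 1.8 to 1.9 per SD. Neither change needs new data, questionnaires or visits.

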## 6.2 Statistical Methods

All subjects, once randomized, will be included in an intention-to-treat analysis and outcomes will be collected even if the caregiver does not engage in the randomly assigned intervention. We will evaluate randomization by testing for covariate (e.g. demographic characteristics) balance between initial treatment groups, and between the re-randomized treatment groups created after the 6-month follow-up. If significant differences are observed, we will adjust for these variables or conduct stratified analyses. All statistical hypothesis tests and power calculations will use a two-sided = 0.05.

**Aim 1:** To test the efficacy of the TCBD intervention compared to usual care for improving primary outcomes [i.e., size-appropriate restraint (dichotomous) and CPaSS (numeric)] at 12 months. We hypothesize greater proportions of children will be using a size-appropriate restraint and higher CPaSS among caregivers in the intervention groups (basic and enhanced) compared with the control group (usual care) at the 12-month assessment. **Statistical Analysis:** Our primary analytic tool for estimating treatment effects will be generalized linear models (GLMs), and for analyses involving joint analysis of multiple follow-up data points, we will use generalized linear mixed models (GLMMs), which allows direct modeling of the correlations between data points (e.g. repeated measurements on individuals), and the inclusion of individuals with incomplete data (e.g. missing time points). The GLM(M) framework also allows simple controlling for confounders (if necessary) through their inclusion in the model as covariates. For the analysis of binary outcomes, we will use logistic GLM(M)s and for numeric outcomes (CPaSS-D) we will initially specify linear (Gaussian) GLM(M)s; this choice will be scrutinized by analyzing model diagnostics. The primary inferential target will be the coefficient for the treatment group indicator, making this effectively equivalent to ANCOVA. Adjustment for the baseline measurement is important for guarding

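### For size-appropriate restraint use, the disparity hypothesis is assessed only on the log-odds scale, so a null or small favourable race interaction could be read as no widening when the percentage-point gap has grown

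*Combined protocol and SAP*

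**What the plan says.** The SubAim in Section 6.2 states the hypothesis: "We hypothesize that disparities in CRS use can be reduced through a tailored intervention". The moderation analysis offered is that "we will evaluate moderation by including interactions between treatment group and sex-, race-, and age-based groupings", within the framework set out for Aim 1. There the plan says: "For the analysis of binary outcomes, we will use logistic GLM(M)s". The main inferential target is the model coefficient, so for size-appropriate restraint use the race interaction is a log ratio of odds ratios. For CPaSS the initial model is linear.

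The plan does not say how a disparity is measured. It plans no race-specific probabilities, no risk difference and no difference in gaps, and gives no power for the race interaction. The mediation analysis concerns effects through the Self-Determination Theory constructs and emotional state, not the racial gap.

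Section 6.1 gives the planning figures: "a) 17% response rate among controls", "25% response rate among TCBD caregivers at 6 Month (with 75% of TCBD caregivers re-randomized", and "only 80% of the target sample (n=204 controls and n=516 TCBD in the initial dichotomy) will be available for analysis at follow-up".

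**The concern.** The hypothesis is about disparities in use, and Aim 1 is framed in proportions of children in a size-appropriate restraint. A natural reading is that a reduced disparity means a smaller difference between groups in that proportion. The planned test answers another question: whether the treatment odds ratio differs by race.

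When rates are below one half and one group starts lower, a common odds ratio adds more percentage points to the group that starts higher. The interaction is then null although the gap in proportions has widened. An interaction modestly in favour of the lower-rate group can also go with a wider gap.

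At stake is what the trial reports on one of its stated hypotheses. If only the logit interaction is reported, a null or small favourable estimate may be summarised as disparities unchanged or slightly improved. With no scale fixed in advance, the choice could also be made after the results are seen.

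**Working it through.** **Inputs from the documents.** Control rate 17%, TCBD rate 25% at Month 6, 75% of TCBD re-randomised, 204 controls and 516 TCBD analysable (Section 6.1); 1:1 re-randomisation (Section 3.2); two-sided 0.05 (Section 6.2).

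**Assumed inputs.** Control rates by race and the minority share are not in the documents. I assume minority families have the lower control rate, the direction that Section 1.1 reports from other samples, and show ranges.

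**1. The plan's own power.** Re-randomised: 0.75 × 516 = 387, so 193.5 enhanced and 516 − 193.5 = 322.5 basic. With a pooled two-proportion z test against 204 controls:
- 29.4% v 17%: power 83.7%, h = 0.296.
- 27.6% v 17%: power 80.9%, h = 0.256.

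Both agree with the stated >80% and h of 0.30 and 0.26.

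**2. Implied odds ratio.** (0.25/0.75)/(0.17/0.83) = 1.627. The plan does not state this value; it follows from the Month 6 assumptions. The rates 27.6% and 29.4% imply 1.86 and 2.03.

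**3. Null interaction, control rates 12% and 22%.** New rate = OR × odds/(1 + OR × odds).
- Minority: odds 0.12/0.88 = 0.1364; × 1.627 = 0.2219; rate 18.2%.
- Majority: odds 0.22/0.78 = 0.2821; × 1.627 = 0.4590; rate 31.5%.
- Gap: 10.0 points under control, 13.3 under TCBD.

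**4. Break-even.** To hold the gap at 10.0, the minority TCBD rate must be 31.46% − 10.0 = 21.46%. Its odds are 0.2732, so the minority odds ratio is 0.2732/0.1364 = 2.00 and the interaction odds ratio is 2.00/1.627 = 1.23. At 1.10 the minority rate is 19.6% and the gap 11.8 points: favourable in sign, still wider.

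**5. Other assumed pairs, common odds ratio 1.627.**

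| Control rates | TCBD rates | Gap, control to TCBD (points) | Break-even interaction OR | Ratio of use rates, control to TCBD |
|---|---|---|---|---|
| 12 / 22 | 18.2 / 31.5 | 10.0 to 13.3 | 1.23 | 1.83 to 1.73 |
| 10 / 20 | 15.3 / 28.9 | 10.0 to 13.6 | 1.29 | 2.00 to 1.89 |
| 14 / 20 | 20.9 / 28.9 | 6.0 to 8.0 | 1.12 | 1.43 to 1.38 |
| 12 / 30 | 18.2 / 41.1 | 18.0 to 22.9 | 1.35 | 2.50 to 2.26 |
| 15 / 25 | 22.3 / 35.2 | 10.0 to 12.9 | 1.17 | 1.67 to 1.58 |
| 16 / 18 | 23.7 / 26.3 | 2.0 to 2.7 | 1.04 | 1.13 to 1.11 |
| 55 / 65 | 66.5 / 75.1 | 10.0 to 8.6 | 0.94 | 1.18 to 1.13 |

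Fixing overall control use at 17% and varying the control gap (5 to 15 points), minority share (25% to 50%) and odds ratio (1.63 to 2.03), the gap widens in every case, by 1.6 to 8.7 points. Break-even runs from 1.10 to 1.98.

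**6. What the trial can show.** At 12/22 with an assumed half share, the cells are 102, 102, 258 and 258.
- SE of the interaction log odds ratio = √Σ 1/(n p(1−p)) = √(0.0928 + 0.0571 + 0.0261 + 0.0180) = 0.44. The smallest significant interaction odds ratio is exp(1.96 × 0.44) = 2.37, well above 1.23.
- SE of the difference in risk differences = √Σ p(1−p)/n = √(0.00104 + 0.00168 + 0.00058 + 0.00084) = 0.064. The 95% half-width is 12.6 points.

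Over the first five pairs with shares of 25% to 50%, the smallest significant interaction is about 2.2 to 3.1 and the half-width about 12 to 15 points. Over the grid in step 5 these are about 2.3 to 4.0 and 11 to 14 points, and power at break-even is 6% to 17%.

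**The case against.** The strongest reply has five parts.

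- **The headline error is unlikely.** A reader might infer that the trial could declare a statistically significant reduction in disparities while the gap widens. The figures do not support that. In every setting with rates near the planning rates, the smallest significant interaction lies above break-even. What is left is the misreading of a null or small estimate, which is a danger on any scale. This stands, and the point is limited accordingly.
- **The percentage-point gap is one valid measure among several.** In the same examples the ratio of use rates narrows. Section 1.1 describes disparities by percentages and rates but also by a ratio, so the documents do not commit to the absolute scale. The logistic interaction is a valid test of whether odds ratios differ by race. This stands too: the test is not wrong, but the hypothesis has no defined measure and nothing is planned on the scale of proportions.
- **The base rates are assumed.** Enrolled families are all selected for suboptimal behaviour or a planned premature transition, so the control gap could be small. At 16/18 the effect is under one point, and at 55/65 it reverses. The Month 6 rates also need not hold at Month 12, where moderation is assessed. All true; it makes the size uncertain and is a reason to fix the scale beforehand.
- **The absolute contrast is imprecise.** It cannot detect a 3.3-point widening. Correct, but its interval would show openly that widening is not excluded.
- **The scope is narrow.** Moderation is a secondary objective, and a reader might extend the criticism to CPaSS. The documents do not support that extension, since its linear interaction is already a difference of differences.

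**Conclusion.** The concern holds for size-appropriate restraint use only. There the sole planned assessment of the disparity hypothesis is a log-odds interaction, which can be null or slightly favourable while the percentage-point gap grows. At assumed control rates of 12% and 22% the gap moves from 10.0 to 13.3 points with no interaction, and an interaction odds ratio of about 1.23 is needed to hold it.

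This rests on minority families having the lower control rate and on rates mostly below 50%. The planning rates fit the second condition; the first is an assumption for this population. The realistic harm is a mistaken statement that the gap has not widened, on a secondary objective. It is a worthwhile, inexpensive correction and does not touch the primary comparison.

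**What to change.** In the SubAim of Section 6.2:

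1. Define the disparity for this outcome, before analysis, as the percentage-point gap between race groups in size-appropriate restraint use at 12 months.
2. From the same logistic model, report standardised probabilities by race and arm, the TCBD-minus-control risk difference in each race group, and the between-race difference in those risk differences with a 95% interval (bootstrap or delta method). State the covariate distribution used for the averaging.
3. Report the logit interaction alongside, and note that the ratio of use rates can move the opposite way.
4. State that the interval is expected to be wide (half-width about 12 to 15 points at 204/516 under the assumed rates and shares) and that failure to detect a change is not evidence of no change.

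The CPaSS moderation analysis needs no change on this account. The cost is a paragraph of SAP wording and a few lines of code, with no new data. The only drawback is an imprecise contrast, which should be acknowledged.
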